2.2. Background

Griseofulvin is an antifungal antibiotic which is active *in vitro* against common dermatophytes. It exerts its antifungal effect by disrupting the cell division spindle apparatus of fungal cells, thereby arresting cell division.

When griseofulvin is given orally for systemic treatment of fungal infections, it enables newly-formed keratin of the skin, hair and nails to resist attack by the fungi. As the new keratin extends, the old infected keratin is shed. Griseofulvin is effective against the dermatophytes causing ringworm (tinea), including: *Microsporum canis*, *T. verrucosum*, *T. mentagrophytes*, *E. floccosum* and *T. rubrum*¹¹

Griseofulvin is not effective in infections caused by *Candida albicans* (monilia), *aspergilli*, *Malassezia furfur* (*Pityriasis versicolor*) and *Nocardia* species¹¹

After oral dosing there is a phase of rapid absorption followed by slower prolonged absorption. Peak plasma levels (0.5 to 1.5 micrograms after a 500 mg oral dose) are achieved by 4 h and are maintained for 10 to 20 h. The absorption of griseofulvin from the gastrointestinal tract is variable and incomplete. On average, less than 50% of the oral

dose is absorbed, but fatty foods and a reduction in particle size will increase the rate and extent of the absorption¹¹

In plasma griseofulvin is approximately 84% bound to plasma proteins, predominantly albumin. There is selective deposition of griseofulvin in newly-formed keratin of hair, nails and skin, which gradually moves to the surface of these appendages. 6-desmethylgriseofulvin or its glucuronide conjugate are metabolites of griseofulvin. The absorbed griseofulvin is excreted in the urine mainly as 6-desmethylgriseofulvin or its glucuronide conjugate. The terminal plasma half-life ranges from 9.5 to 21 h, there being considerable intersubject variability¹¹

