A validated LC-MS/MS analytical methodology will be used for the determination of Griseofulvin from the human plasma samples. Validation of the methodology will be carried out in accordance with applicable guidelines and the applicable SOP of analytical facility of Accutest Research Laboratories (I) Pvt. Ltd which are designed in accordance with the regulatory guidelines such as USFDA, EMEA, DCGI etc.

The following parameters (as applicable for BE demonstration and for dose proportionality) will be calculated for each participant-formulation combination using the non-compartmental model by using statistical package SAS[®] 9.2 or higher version:

All concentration values below the limit of quantification (BLQ) will be set to zero for the estimation of pharmacokinetic parameters.

If the pre-dose value is >5 percent of C_{max} , the respective period of that subject will be dropped from all PK evaluations and statistical evaluations

The pharmacokinetic samples of subjects dropped out or withdrawn due to vomiting / diarrhoea or any other reason will not be analyzed for the respective study period. The samples of subjects completing at least 2 periods of the study will be subjected to statistical analysis.

Depending upon availability of data, the subject will be either included in bioequivalence evaluation or dose proportionality evaluation.

Primary parameters

C_{max}	Maximum observed drug concentration during the study.
AUC_{0-t}	Area under the plasma concentration - time curve measured to the last quantifiable concentration, using the linear trapezoidal rule.
AUC_{0-inf}	AUC_{0-t} plus additional area extrapolated to infinity, calculated using the formula $AUC_{0-t} + C_t/K_{el}$, where C_t is the last measurable drug concentration and K_{el} is the elimination rate constant.

Secondary parameters

T_{max}	Time to observe maximum drug concentration. If the maximum value occurs at more than 1 time point, T_{max} is defined as the first time point with this value.
AUC_{0-t} / AUC_{0-inf}	Ratio of AUC_{0-t} and AUC_{0-inf}
Residual area	Extrapolated area $(AUC_{0-inf} - AUC_{0-t}) / AUC_{0-inf}$

K_{el}	Apparent first – order terminal elimination rate constant calculated from a semi-log plot of the plasma concentration versus time curve, using the method of least square regression.
$t_{1/2}$	Terminal half-life as determined by quotient $0.693/K_{el}$

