Vd	Fluid volume that would require to contain the whole drug in the body at the same conc. found in the plasma is given by formula, $Dose / (K_{el} \times AUC_{0-inf})$
CL	Clearance of a given individual in the measure of his body capacity to eliminate a drug and is given by formula $Dose / AUC_{0-inf}$

The pharmacokinetic parameters will not be calculated in case of inconclusive concentration time profile (e.g. lack of sufficient measurable concentrations).

No value of K_{el} , Residual area, AUC_{0-t}/AUC_{0-inf} , AUC_{0-inf} , Vd, CL and $t_{1/2}$ will be reported for cases that do not exhibit a terminal log-linear phase in the concentration versus time profile.

Name and address details of Biostatistician (For PK analysis):

Name: [name], M.Sc. (Statistics)/ [name] (B. Com, SAS Programmer)

Address: Statistical Facility:

Accutest Research Laboratories (I) Pvt. Ltd.,
[name],
[name],
Maharashtra, INDIA.

Tel: PPD

Fax: PPD

Email:

PPD

All the procedures of PK analysis will be carried out in accordance with applicable guidelines and the applicable SOP of statistical facility of Accutest Research Laboratories (I) Pvt. Ltd.

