9. STATISTICAL CONSIDERATIONS

9.1. Statistical Hypotheses

Null Hypothesis Testing

For BE Demonstration (T1 vs. R)

Null hypothesis H0 and alternative hypothesis H1 can be written in multiplicative form:

$$H0: m_{\text{test } 1} / m_{\text{ref}} < L \text{ or } m_{\text{test } 1} / m_{\text{ref}} > U$$

$$H1: L \leq m_{\text{test } 1} / m_{\text{ref}} \leq U$$

Where L (Lower Limit) = 80.00% and U (Upper Limit) = 125.00%,

$m_{\text{test } 1}$ = geometric least-squares means for test product (Griseofulvin 500mg tablets)

m_{ref} = geometric least-squares means for reference product (Griseofulvin tablets, 500 mg (Grisovin))

The type I error will be set to $\alpha = 5\%$ and therefore 90% (two-tails) confidence intervals will be provided together with indication whether the null hypothesis of non-equivalence for appropriate parameter can be rejected.

For For dose proportionality (T2 vs. T1)

Null hypothesis H0 and alternative hypothesis H1 can be written in multiplicative form:

$$H0: m_{\text{test } 2} / m_{\text{test } 1} < L \text{ or } m_{\text{test } 2} / m_{\text{test } 1} > U$$

$$H1: L \leq m_{\text{test } 2} / m_{\text{test } 1} \leq U$$

Where L=80.00% and U=125.00%,

$m_{\text{test } 1}$ = geometric least-squares means for test product (Griseofulvin 500 mg tablets)

$m_{\text{test } 2}$ = geometric least-squares means for reference product (Griseofulvin 250 mg tablets)

The type I error will be set to $\alpha = 5\%$ and therefore 90% (two-tails) confidence intervals will be provided together with indication whether the null hypothesis of non-equivalence for appropriate parameter can be rejected.

Step 1: For BE Demonstration (T1 vs. R):

PROC MIXED procedure will be used for analysis of variance and the estimation of least square mean differences (Test (T1) - Reference (R)) of the test (T1) and reference formulations on the log-transformed pharmacokinetic parameters C_{\max} , AUC_{0-t} and AUC_{0-inf} . The corresponding standard errors of the differences will also be computed. Based on these parameters, the 90% confidence intervals will be constructed for the least square mean differences of log-transformed parameters C_{\max} , AUC_{0-t} and AUC_{0-inf} . The antilog (or exponential) of the limits obtained from the log-transformed data will give the 90% confidence interval for the ratio of geometric means of test (T1) and reference (R) products.

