If the 90% confidence interval of geometric mean ratio of C_{\max} , AUC_{0-t} and AUC_{0-inf} between test (T1) and reference (R) products falls within the range of 80.00% to 125.00% for Griseofulvin, the null hypothesis will be rejected. In this case the test product (T1) will be concluded as bioequivalent to the reference product R.

If bioequivalence is demonstrated between the Test product (T1) and reference product (R), the following step II will be followed.

Step 2: For dose proportionality (T2 vs. T1):

Dose normalization will be done for test product T2 for AUC_{0-t} and C_{\max} parameter by multiplying with the correction factor 2.

PROC MIXED procedure will be used for analysis of variance and the estimation of least square mean differences (Test (T2) - Test (T1)) of the test (T2) and test (T1) products on the log-transformed pharmacokinetic parameter AUC_{0-t} and C_{\max} . The corresponding standard errors of the differences will also be computed. Based on these parameters, the 90% confidence intervals will be constructed for the least square mean differences of log-transformed parameter AUC_{0-t} and C_{\max} . The antilog (or exponential) of the limits obtained from the log-transformed data will give the 90% confidence interval for the ratio of geometric means of test (T2) and test (T1) products.

Null hypothesis will be rejected if the 90% confidence interval of geometric mean ratio of AUC_{0-t} and C_{\max} between test (T2) and test (T1) products falls within the range of 80.00% to 125.00% for Griseofulvin.

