9.4.1. Analysis of Variance

Step 1: For BE Demonstration (T1 vs. R):

ANOVA will be performed using PROC MIXED on log-transformed pharmacokinetics parameters C_{\max} , AUC_{0-t} and AUC_{0-inf} at α level of 0.05.

The analysis of variance model will include sequences, period and treatment as fixed factors and participants nested within sequence as random factor [i.e. Model LC_{\max} or $LAUC_{0-t}$ or $LAUC_{0-inf}$ = sequence period treatment (fixed factors) and random: Participant (Sequence) (random factor)].

A separate ANOVA model will be used to analyze each of the parameters. All main effects will be tested against the residual error (mean square error) from the ANOVA model as the error term.

Each analysis of variance will also include calculation of least-square means, adjusted differences between formulation means and the standard error associated with these differences.

Step 2: For dose proportionality (T2 vs. T1):

ANOVA will be performed using PROC MIXED on log-transformed pharmacokinetics parameter AUC_{0-t} and C_{\max} at the α level of 0.05.

The analysis of variance model will include sequences, period and treatment as fixed factors and participants nested within sequence as random factor [i.e. Model $LAUC_{0-t}$ or LC_{\max} = sequence period treatment (fixed factors) and random: Participant (Sequence) (random factor)].

A separate ANOVA model will be used to analyze each of the parameters. All main effects will be tested against the residual error (mean square error) from the ANOVA model as the error term.

Each analysis of variance will also include calculation of least-square means, adjusted differences between formulation means and the standard error associated with these differences.

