9.4.4. Accountability Procedure

9.4.4.1. Treatment of Missing Values

Missing sample values (MSV) or non-reportable values (NRV), of the plasma concentration data, will be represented as MSV and NRV in the plasma concentration tables and reasons for their missing will be documented. Any BLQ value occurring between two measurable concentration values will also be treated as missing sample (MS). These missing values will be treated as „missing values“ for Pharmacokinetic and statistical analysis. All the procedures will be performed in accordance with current version of SOP for „Calculation of Pharmacokinetic Parameters“.

For participants with missing or non-reportable concentrations for three or more of the last samples, only the C_{max} and T_{max} will be presented and included in the statistical analysis. Other PK parameters will not be reported.

Data from the participants with missing concentrations values (missed blood draws, lost samples, samples unable to be quantified) may be used if pharmacokinetic parameters can be estimated using the remaining data points. Otherwise, concentration data from these participants will be excluded from the final analysis.

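### Protocol 8.5 withholds Cmax and AUC0-t when too few concentrations are measurable, so a near-complete absorption failure leaves both primary comparisons because of its own value, and no planned analysis retains it

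*Protocol*

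**What the plan says.** Protocol 8.5, after the parameter definitions, and the notes to SAP 8.1.1.2 carry the same rule: "The pharmacokinetic parameters will not be calculated in case of inconclusive concentration time profile (e.g. lack of sufficient measurable concentrations"). Neither gives a minimum count, a decision-maker or a cap.

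The next sentence in both documents is narrower. It lists Kel, AUC0-inf, half-life and the other quantities derived from Kel, and says that no value "will be reported for cases that do not exhibit a terminal log-linear phase in the concentration versus time profile". Cmax and AUC0-t are not on that list.

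Other rules bear on the same profiles:
- Protocol 8.5: "All concentration values below the limit of quantification (BLQ) will be set to zero for the estimation of pharmacokinetic parameters".
- Protocol 9.4.4.1 (and SAP 10.5.2) treats a BLQ value between two measurable values as missing. It keeps Cmax when three or more of the last samples are missing. Data with missed, lost or unquantifiable samples "may be used if pharmacokinetic parameters can be estimated using the remaining data points".
- Protocol 9.4.4.3 plans an analysis with and without excluded data for statistical outliers only.
- SAP 10.5.2 requires exclusions to be documented with a reason. SAP 8.1.4.1 makes the PK analyses conditional on well-defined profiles.

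**The concern.** Most legitimate reasons for losing a period have their own rule: missed or lost samples (9.4.4.1), vomiting or diarrhoea (7.2 and 8.5), a high pre-dose value (8.5) and no terminal phase (8.5). A mouth check (6.4) makes non-ingestion unlikely. What this sentence chiefly adds is a dose that was taken, sampled and assayed and yielded very little drug. That is an outcome, not missing data.

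The rule is not needed for the two endpoints that it removes. One measurable value gives Cmax, and AUC0-t can be summed with BLQ values as zero.

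T1 and T2 are new formulations of a low-solubility drug, and Protocol 2.2 says: "The absorption of griseofulvin from the gastrointestinal tract is variable and incomplete". If a tablet occasionally fails to release, the comparison would rest on the periods in which it worked. Blinding the person who makes the call would not help, because the selection is on the measured exposure.

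**Working it through.** **Inputs.** Protocol 9.2: 27 evaluable (9 per sequence), 90% power, ratio 0.95, within-subject CV 21%. Protocol 9.4.1: "ANOVA will be performed using PROC MIXED on log-transformed pharmacokinetics parameters". Protocol 9.1: limits 80.00–125.00% and 90% intervals. Protocol 2.2: peaks of 0.5–1.5 micrograms after 500 mg, taken here as per mL. Assumptions, not in the documents: the assay limit, the fraction r of normal exposure in a failed period, and the failure rate p per T1 dose.

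**1. The plan's own figure.** Log-scale SD = √ln(1 + 0.21²) = 0.2077. Two one-sided tests at n = 27 have power 0.911 in the three-treatment model (df = 2n − 4 = 50) and 0.904 in a pairwise analysis (df = n − 2 = 25). The stated 90% is reproduced, so the sample size is not in dispute.

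**2. Which profiles the rule would catch.** Normal peaks are 500–1500 ng/mL. At 1–2% of exposure the peak is 5–30 ng/mL, at or near an assumed limit of 5–20 ng/mL. At 5–10% it is 25–150 ng/mL, which stays measurable unless the limit is near 50 ng/mL. The rule would therefore mainly catch near-complete failure. If exposure is proportional to dose, T2 peaks are half as high and reach the rule sooner.

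**3. One failed T1 period, by hand (r = 0.02, pairwise, 24 df).** The SD of a T1−R log difference is √2 × 0.2077 = 0.2938 (variance 0.0863).
- Kept: ratio = 0.95 × 0.02^(1/27) = 0.822. Residual variance ≈ 0.0863 + (ln 0.02)² × (8/9)/24 = 0.653. SE = √(0.653/27) = 0.1555. Half-width = 1.711 × 0.1555 = 0.266. The 90% CI is about 0.63–1.07, which fails.
- Deleted (9, 9 and 8 per sequence, 23 df): SE = (0.2938/3) × √(1/9 + 1/9 + 1/8) = 0.0577. Half-width = 1.714 × 0.0577 = 0.099. The 90% CI is about 0.86–1.05, which passes.

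**4. Simulated pass rates, one failed T1 period, ratio otherwise 0.95.** Ranges cover the pairwise and three-treatment models.

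| Exposure in that period | Ratio if kept | Pass, kept | Pass, deleted |
|---|---|---|---|
| 1–2% | 0.80–0.82 | 0.00 | about 0.90 |
| 5% | 0.85 | 0.00–0.02 | 0.89–0.90 |
| 10% | 0.87 | 0.07–0.15 | 0.89–0.90 |

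One failed T2 period at 5% of exposure gives 0.02 kept and 0.90 deleted for T2/T1.

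**5. How often.** The chance of at least one failed T1 period is 1 − (1 − p)^m. For m = 27 to 36 it is 5–7% at p = 0.2%, 13–17% at 0.5% and 24–30% at 1%.

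**6. Is that product equivalent?** True ratio = 0.95 × r^p. For p = 0.2–1% and r = 0.01–0.10 it runs from 0.907 to 0.946, inside the limits. The overall pass rate with failures kept is about (1 − p)^27 × 0.911 + 27p(1 − p)^26 × 0.018 at r = 0.05. This is 0.86 at p = 0.2% and 0.70 at p = 1%, against 0.89–0.90 deleted.

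**7. Where the error rate is at issue.** A true ratio of 0.80 needs p = ln(0.80/0.95)/ln r, which is 3.7% (r = 0.01), 5.7% (r = 0.05) or 7.5% (r = 0.10). Deletion then passes about 0.86–0.90 of trials. Keeping the periods passes 0.33, 0.20 and 0.14, also above 0.05. This is mostly because some trials see no failure: at r = 0.05, (1 − 0.0574)^27 = 0.20.

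**8. Direction.** With one failed T1 period at r = 0.05, kept versus deleted is 0.36 versus 0.91 at a ratio of 1.05, 0.54 versus 0.70 at 1.10 and 0.50 versus 0.40 at 1.15. At r = 0.10 it is already reversed at 1.10 (0.80 versus 0.72). For one failed R period at r = 0.05 and ratio 0.95, it is 0.35 versus 0.91.

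**9. Would the outlier rule bring the period back?** Section 9.4.4.3 works on untransformed values. For lognormal data with median 1, Q1 − 3 × IQR is 0.026 at a total CV of 21% and negative at 30–60%, so low values are rarely flagged. A parameter that was never calculated cannot be flagged at all.

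**The case against.** The strongest reply is that the rule is vague rather than aimed at low exposure. The trigger is an inconclusive profile and low counts are only an example. Missing samples can cause it too, section 9.4.4.1 leaves room to use unquantifiable data, and the SOPs to which the plan defers may hold a criterion. This stands as far as it goes: the documents do not show that the rule will be used to drop failures. Its one example, however, is too few measurable concentrations, and nothing in either document exempts Cmax and AUC0-t.

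A reader might infer that the 5% error rate is lost outright. The documents do not support that. At 0.2–1% failures the product meets the equivalence definition in Protocol 9.1, and passing it is correct. The contrast of 0% with 90% is conditional on a failure having occurred.

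A reader might also infer that deletion always favours the sponsor. It does so at the planned ratio and up to about 1.05. It can reverse when T1 otherwise runs about 10–15% or more above R, which is not remote because Protocol 2.1 says that the new formulations aim at better absorption. The rule covers R as well.

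Finally, the 5% and 10% rows matter only if the assay limit is high. That is accepted; the conclusion rests on the 1–2% row.

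**Conclusion.** The concern holds in this bounded form. The plan contains an undefined, outcome-dependent deletion from both primary comparisons, and only documentation of the exclusion is planned. Its reach is probably confined to near-complete failure. Within that reach one T1 period decides the trial: about 0% pass kept and about 90% deleted, with the estimated ratio at 0.80–0.82 or 0.95. At assumed failure rates of 0.2–1% the effect is on the estimate and the pass rate, not on a false claim. A breach of the error rate attributable to deletion needs failures in about 4–7.5% of T1 doses, a frequency for which the documents give no evidence. The assay limit, the exposure fractions and the failure rates are assumptions; the sample size, CV, ratio and limits are the plan's.

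**What to change.** In Protocol 8.5 and SAP 8.1.1.2:
- Limit the sentence to Kel-dependent parameters.
- Calculate Cmax and AUC0-t for every period in which the dose was taken, the samples were assayed and at least one post-dose concentration is quantifiable. Reconcile the BLQ rules of Protocol 8.5 and 9.4.4.1: leading and trailing BLQ as zero, embedded BLQ as missing. The SAP carries only the second of these and should state both.
- Keep such T1 and T2 periods in the primary analysis. Report T1/R and T2/T1 with and without all low-exposure periods, R included, with counts by product.
- A period with no quantifiable post-dose value has no logarithm. Report it by product, and include it in a pre-specified sensitivity analysis with a stated value based on the assay limit, one for Cmax and one for AUC0-t. Any such value is partly arbitrary and can dominate the result, so it belongs in a sensitivity analysis.

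Bioequivalence requires all three parameters to pass, so keeping the period in Cmax and AUC0-t is enough for a failure to show even when AUC0-inf is withheld.

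The cost is wording in two documents and a few extra runs. The downside to state is that a handling accident on a test tablet would stay in the primary analysis and could cost the claim. The analysis without it would show this.

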8.6. Pharmacodynamics

Pharmacodynamic parameters are not evaluated in this study.

8.7. Genetics

Genetics are not evaluated in this study.

8.8. Biomarkers

Biomarkers are not evaluated in this study.

8.9. Immunogenicity Assessments

Not Applicable.

8.10. [Health Economics] OR [Medical Resource Utilization and Health Economics]

Health Economics/Medical Resource Utilization and Health Economics parameters are not evaluated in this study.

9. STATISTICAL CONSIDERATIONS

9.1. Statistical Hypotheses

Null Hypothesis Testing

For BE Demonstration (T1 vs. R)

Null hypothesis H0 and alternative hypothesis H1 can be written in multiplicative form:

$$H0: m_{\text{test } 1} / m_{\text{ref}} < L \text{ or } m_{\text{test } 1} / m_{\text{ref}} > U$$

$$H1: L \leq m_{\text{test } 1} / m_{\text{ref}} \leq U$$

Where L (Lower Limit) = 80.00% and U (Upper Limit) = 125.00%,

$m_{\text{test } 1}$ = geometric least-squares means for test product (Griseofulvin 500mg tablets)

m_{ref} = geometric least-squares means for reference product (Griseofulvin tablets, 500 mg (Grisovin))

The type I error will be set to $\alpha = 5\%$ and therefore 90% (two-tails) confidence intervals will be provided together with indication whether the null hypothesis of non-equivalence for appropriate parameter can be rejected.

For For dose proportionality (T2 vs. T1)

Null hypothesis H0 and alternative hypothesis H1 can be written in multiplicative form:

$$H0: m_{\text{test } 2} / m_{\text{test } 1} < L \text{ or } m_{\text{test } 2} / m_{\text{test } 1} > U$$

$$H1: L \leq m_{\text{test } 2} / m_{\text{test } 1} \leq U$$

Where L=80.00% and U=125.00%,

$m_{\text{test } 1}$ = geometric least-squares means for test product (Griseofulvin 500 mg tablets)

$m_{\text{test } 2}$ = geometric least-squares means for reference product (Griseofulvin 250 mg tablets)

The type I error will be set to $\alpha = 5\%$ and therefore 90% (two-tails) confidence intervals will be provided together with indication whether the null hypothesis of non-equivalence for appropriate parameter can be rejected.

Step 1: For BE Demonstration (T1 vs. R):

PROC MIXED procedure will be used for analysis of variance and the estimation of least square mean differences (Test (T1) - Reference (R)) of the test (T1) and reference formulations on the log-transformed pharmacokinetic parameters C_{\max} , AUC_{0-t} and AUC_{0-inf} . The corresponding standard errors of the differences will also be computed. Based on these parameters, the 90% confidence intervals will be constructed for the least square mean differences of log-transformed parameters C_{\max} , AUC_{0-t} and AUC_{0-inf} . The antilog (or exponential) of the limits obtained from the log-transformed data will give the 90% confidence interval for the ratio of geometric means of test (T1) and reference (R) products.

If the 90% confidence interval of geometric mean ratio of C_{\max} , AUC_{0-t} and AUC_{0-inf} between test (T1) and reference (R) products falls within the range of 80.00% to 125.00% for Griseofulvin, the null hypothesis will be rejected. In this case the test product (T1) will be concluded as bioequivalent to the reference product R.

If bioequivalence is demonstrated between the Test product (T1) and reference product (R), the following step II will be followed.

Step 2: For dose proportionality (T2 vs. T1):

Dose normalization will be done for test product T2 for AUC_{0-t} and C_{\max} parameter by multiplying with the correction factor 2.

PROC MIXED procedure will be used for analysis of variance and the estimation of least square mean differences (Test (T2) - Test (T1)) of the test (T2) and test (T1) products on the log-transformed pharmacokinetic parameter AUC_{0-t} and C_{\max} . The corresponding standard errors of the differences will also be computed. Based on these parameters, the 90% confidence intervals will be constructed for the least square mean differences of log-transformed parameter AUC_{0-t} and C_{\max} . The antilog (or exponential) of the limits obtained from the log-transformed data will give the 90% confidence interval for the ratio of geometric means of test (T2) and test (T1) products.

Null hypothesis will be rejected if the 90% confidence interval of geometric mean ratio of AUC_{0-t} and C_{\max} between test (T2) and test (T1) products falls within the range of 80.00% to 125.00% for Griseofulvin.

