8.5. Pharmacokinetics

Whole blood samples of approximately 5 mL will be collected for measurement of plasma concentrations of Griseofulvin as specified in the SoA.

An intravenous cannula will be inserted into the participant's arm for the collection of the blood samples before the pre-dose blood sample and up to 24.00 hrs post-dose. If difficulties occur in blood withdrawal or if the participant is not feeling comfortable with the cannula, then the cannula will be removed before 24.00 hrs post-dose and the remaining blood samples will be collected through fresh vein puncture or by recannulation. When meals, vitals and sample collections coincide, samples will be collected first followed by vitals and then meal will be served.

Before every blood sample collection, 0.2 mL of blood present in the intravenous cannula will be discarded during the use of the intravenous cannula except for the ambulatory sample. Also after every blood sample collection, 0.2 mL of heparinised saline (by mixing 1 mL of 5000 IU/5mL of heparin with 500 mL of normal saline) will be injected into the intravenous cannula.

Twenty-Two (22) blood samples will be collected in Na-Heparin vacutainers at pre-dose (collected within 01.00 hour prior to dosing), 00.50, 01.00, 01.50, 02.00, 02.50, 03.00, 03.50, 04.00, 04.50, 05.00, 05.50, 06.00, 06.50, 07.00, 08.00, 10.00, 12.00, 24.00, 48.00, 72.00 and 96.00 hours post dose.

Note: The actual time of blood collection (24 hour clock) will be considered for calculation of PK parameters. Duration of 2 minutes is required for the completion of procedure of blood sample collection. Hence, the reason for deviation up to 2 minutes for the blood sample collection activity need not be documented. However, the reason for delay beyond 2 minutes will be documented in the case record form and/or other document.

Blood samples after 24 hrs will be collected on ambulatory basis through direct vein puncture. The actual end-point time of collection of each blood sample will be recorded in the CRF.

Ambulatory blood sample will be collected up to 04.00 hrs from the scheduled time of blood sample collection. If the participant reports for blood sample collection beyond 04.00 hrs, the blood sample will not be collected, and the participant will be requested to come for the next ambulatory sample (if any).

Approximate blood loss during the study:

		Males	Females
Total PK blood samples (66 x 5 mL)	:	330 mL	330 mL
Pre study screening	:	Upto 10 mL	Upto10 mL

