9.2. Sample Size Determination

*Intra subject variability of 21% was chosen as clinically meaningful estimate based on the Sensitivity analysis on the variability estimates of 17% performed using 95th percentile approach.⁸

A sample size of 27 participants (adjusted for 9 subjects per sequence) without dropouts will be appropriate to provide 90% power for 90% confidence interval for the ratio of

Test to Reference for log-transformed C_{max} and AUC to lie within the acceptance region of bioequivalence 80% to 125%. This estimate is based on the ratio of Test product and Reference product is 0.95 and intra subject variability of 21% of Griseofulvin.

A sample size of 36 subjects are proposed for this 3-way cross-over study considering the dropouts and withdrawal of participants.

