8.1.2. Summary Measure

Parameters C_{max} , AUC_{0-t} and AUC_{0-inf} will be applicable for BE demonstration and Parameters C_{max} , and AUC_{0-t} for dose proportionality. These parameters will be calculated for each participant-formulation combination using the non-compartmental model by using statistical package SAS® 9.4

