10.8.1. Study Population Tables

10.8.2. Pharmacokinetic Tables

The SAS System, Version: 9.4
 Accutest Research Laboratories (I) Pvt. Ltd.
 Study Code -
 Individual Pharmacokinetic Parameters of Griseofulvin for 'Test Products (T1 and T2)'

Subject	Sequence	Period	Treatment	Cmax (ng/mL)	Tmax (hrs)	AUC(0-t) (ng*hr/mL)	AUC(0-inf) (ng*hr/mL)	AUC Ratio (%)	Residual Area (%)	Kel (hrs-1)	Kel_First (hrs)	Kel_Last (hrs)	Thalf (hrs)

The SAS System, Version: 9.4
 Accutest Research Laboratories (I) Pvt. Ltd.
 Study Code -
 Individual Pharmacokinetic Parameters of Griseofulvin for 'Reference Product (R)'

Subject	Sequence	Period	Treatment	Cmax (ng/mL)	Tmax (hrs)	AUC(0-t) (ng*hr/mL)	AUC(0-inf) (ng*hr/mL)	AUC Ratio (%)	Residual Area (%)	Kel (hrs-1)	Kel_First (hrs)	Kel_Last (hrs)	Thalf (hrs)

[figure not shown]

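### Does doubling a 250 mg AUC0-t that ends at its own last quantifiable sample bias the dose-proportionality test enough to need a common-interval AUC?

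*Protocol*

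**What the plan says.** Protocol 8.5 and SAP 8.1.1.2 define AUC0-t identically, as the area under the "curve measured to the last quantifiable concentration, using the linear trapezoidal rule". Each profile therefore has its own end point.

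Protocol 9.1 (Step 2) and SAP 2.4 apply the dose normalisation, "parameter by multiplying with the correction factor 2", to T2 only. They then require the 90% confidence interval for T2/T1 to lie within 80.00–125.00%. Protocol 9.4.3 requires this for AUC0-t and for Cmax, and Step 2 is reached only if T1 has been shown bioequivalent to the reference (R).

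SAP 8.1.2 assigns parameters to comparisons: the three of Cmax, AUC0-t and AUC0-inf "will be applicable for BE demonstration and Parameters" Cmax and AUC0-t for dose proportionality. Neither document plans a T2/T1 comparison of AUC0-inf or of an AUC over a shared interval.

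Both documents do derive AUC0-inf, the AUC ratio and the residual area for every profile. The first table shell in SAP 10.8.2, "Individual Pharmacokinetic Parameters of Griseofulvin for 'Test Products (T1 and T2)'", lists them per participant together with the first and last times used for the elimination rate.

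**The concern.** The two profiles differ twofold in concentration but face the same quantification limit. If kinetics are proportional, the 250 mg curve meets that limit one half-life before the 500 mg curve; Protocol 2.2 puts the half-life at 9.5–21 h. The late samples are at 24, 48, 72 and 96 h. When one of them falls in the gap, T2 loses a whole 24 h segment that T1 keeps, and doubling does not restore it.

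The T1/R comparison has no such built-in asymmetry, because the doses are equal, and it is also tested on AUC0-inf. T2 has no reference product, so Step 2 is its only formal comparison. A systematic downward shift there could cost power near 80%, or hide part of a true excess near 125%.

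**Working it through.** **1. Reproduce the plan's own figure.** Protocol 9.2 gives 27 evaluable participants for 90% power: "This estimate is based on the ratio of Test product and Reference product is 0.95 and intra subject variability of 21% of Griseofulvin".

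- Log-scale SD: s = √ln(1 + 0.21²) = 0.2077.
- Standard error of a treatment difference: 0.2077 × √(2/27) = 0.0565.
- Exact power of two one-sided 5% tests at ratio 0.95: 91.1% with residual df 2n − 4 = 50, or 90.4% with df n − 2 = 25. The stated figure reproduces. Later power figures use df 50.

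**2. One profile, to show the mechanism.** Assume a 500 mg Cmax of 1000 ng/mL reached at 4 h, half-life 15 h, and a limit of 12.5 ng/mL.

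- T1: C(72) = 1000 × 2^(−68/15) = 43.2 ng/mL and C(96) = 1000 × 2^(−92/15) = 14.2 ng/mL. Both are quantifiable, so T1 ends at 96 h.
- T2 under exact proportionality: 21.6 and 7.1 ng/mL, so T2 ends at 72 h.
- Segment lost: 24 × (43.2 + 14.2)/2 ≈ 689, against a T1 AUC0-t of about 24,329 ng·h/mL.
- Ratio: 1 − 689/24,329 = 0.972.

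Where both profiles end at the same sample the ratio is exactly 1, so the average shift is smaller than in this example.

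**3. Average over participants, exact proportionality.** From Protocol 2.2: half-life uniform on 9.5–21 h, and 500 mg Cmax uniform on 500–1500 ng/mL (the stated 0.5–1.5 micrograms, read as per mL). From Protocol 8.5: the 22 sampling times and the linear trapezoid. Assumptions: linear rise to 4 h, peak held to 4, 10 or 20 h, mono-exponential decline, and the quantification limit, for which a range is shown. There were 60,000 draws per setting. Ranges run over the three plateau lengths.

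| Assumed limit (ng/mL) | Expected T2/T1 | T2 ends earlier | AUC0-t power, true ratio 1.00 | AUC0-t power, true ratio 0.95 |
|---|---|---|---|---|
| none | 1.000 | – | 97.5% | 91% |
| 1 | 0.9995–1.000 | 0–7% | 97.5% | 91% |
| 5 | 0.994–0.998 | 13–23% | 97.5% | 89–91% |
| 12.5 | 0.979–0.991 | 25–43% | about 96.5–97% | 84–88% |
| 20 | 0.959–0.979 | 41–55% | 93–96.5% | 73–84% |

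Power uses n = 27 and CV 21%, with the true ratio multiplied by the expected ratio in column 2.

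**4. How far up the table the trial could sit.** The shift depends only on limit/Cmax. Dosing follows a high-fat breakfast, and Protocol 2.2 says that less than half the "dose is absorbed, but fatty foods and a reduction in particle size will increase the rate and extent of the absorption". Protocol 2.1 adds that the new tablets are formulated for better absorption. If Cmax is doubled (an assumption), the ratio is 0.991–0.997 at 12.5 ng/mL and 0.984–0.994 at 20 ng/mL.

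Protocol 8.5 also drops a period whose pre-dose value exceeds 5% of Cmax. For T2, with Cmax 250–750 ng/mL, 5% is 12.5–37.5 ng/mL. With a limit of 20 ng/mL, 5% of Cmax would be unmeasurable whenever Cmax is below 400 ng/mL, a share of (400 − 250)/500 = 30%. That does not fix the limit, but a limit of 20 ng/mL fits the plan poorly.

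**5. Sample size and CV.** Take the worst 12.5 ng/mL ratio (0.979) and a true ratio of 0.95. Power is 84% with 27 participants, 87% with 30, 90% with 33 and 92% with all 36 randomised. With the source CV of 17% instead of the inflated 21%, it is 94% at 27.

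**6. False acceptance.** If AUC and Cmax are both truly 1.25, Cmax passes 5.0% of the time and is not truncated, so the joint pass rate cannot exceed 5%. Simulation at 12.5–20 ng/mL gave 0.3–4.4%, depending on the AUC–Cmax correlation.

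**The case for a change.** The strongest case for acting is that the limit is unknown, so nobody can show from the documents that the shift is negligible. A borderline AUC0-t result near 80% could not be separated from truncation by any pre-specified analysis, and one added later would look data-driven. A common-interval AUC returns the ratio to 1.000 under proportionality, needs no new samples, and takes a few lines of SAP text.

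Much of this stands: the direction is right, the limit is missing, and the cost is low. There is also one pattern in which the Cmax safeguard does not help. If AUC were non-proportional at 1.25 and Cmax were proportional, AUC0-t alone would pass about 6% of the time at the worst 5 ng/mL ratio, 10% at the worst 12.5 ng/mL ratio and 18% at the worst 20 ng/mL ratio. The documents give no sign of that pattern.

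Against acting:

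- The loss of power is material only at a true T2/T1 ratio near 0.95. That figure is the planning ratio for test against reference; no ratio is planned for T2/T1.
- The common-interval AUC has weaknesses. Its cut point is set by the data. It would discard real 500 mg exposure if that tail were longer than proportional. It also needs interpolation, because of the ambulatory window: "Ambulatory blood sample will be collected up to 04.00 hrs from the scheduled time of blood sample collection".
- AUC0-inf and residual area are listed for each T1 and T2 profile. A reader facing a borderline result can see whether T2 profiles stop early and how much area lies beyond the last sample. At high limits AUC0-inf will be missing for some profiles.
- Individual ratios are not bounded by 1 in any case. Within-subject variation sees to that, and so occasionally can the Protocol 9.4.4.1 rule for a value below the limit between two measurable ones.

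**Conclusion.** No change follows, because the remedy brings no real gain. The plan defines AUC0-t clearly and identically in both documents. Its truncation lowers the expected T2/T1 ratio by at most about 0.6% for an assumed limit up to 5 ng/mL and by about 1–2% at 12.5 ng/mL, and by about half of that or less if fed Cmax is doubled. At a true ratio of 1.00, power for AUC0-t stays at about 96.5% or more across that range. The larger effects need a limit near 20 ng/mL with no rise in Cmax from food or formulation, or a true ratio already near 0.95.

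A common-interval AUC would have to be supportive only, with AUC0-t still deciding, so the formal conclusion would be the same with or without it. The SAP already allows additional parameters, and analysts may show this one or a T2/T1 interval for AUC0-inf if they wish; that would be an extra display.

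This rests on the assumed quantification limits, the simplified profile shape, and the background Cmax and half-life ranges. A limit well above 20 ng/mL would make the shift larger than stated here.
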